8.4 Benefit and risk assessment

8.4.1 Benefit for the patient

If the hypothesis is correct, participating patients receiving the study medication will benefit from a reduced risk of developing liver injury due to long term parenteral nutrition. They will benefit from a improved long term neurodevelopment.

8.4.2 Risk for the patient

The drug under investigation fulfilled the criteria for registration for application in preterm infants. Therefore, risk for patients receiving the study drug should not be higher compared to standard care. In the worst case we expect that there will be no benefit.

8.5 Study procedures

8.5.1 General rules for trial procedures

- All study measures like blood sampling and measurements (ultrasound etc.) have to be documented with date (dd:mmm:yyyy).
- In case several study procedures are scheduled at the same time point, there is no specific sequence that should be followed.
- The dates of all procedures should be according to the protocol. The time margins mentioned in the study flow chart are admissible. If for any reason, a study procedure is not performed within scheduled margins a protocol deviation should be noted, and the procedure should be performed as soon as possible or as adequate.
- If it is necessary for organizational reasons, it is admissible to perform procedures which are scheduled for one visit at two different time points. Allowed time margins should thereby not be exceeded.

8.5.2 Screening investigation

At screening, the patient's demographic data and lab results (see Section 7.1.2 and 7.1.3 Inclusion and Exclusion Criteria) will be evaluated for eligibility to the study.

8.5.3 End-of-study (EOS) examination

At discharge of the patient from hospital, patients undergo the end-of-study examination that entails Weight, crown heel length, head circumference and a basic blood test (red and white blood count, liver function tests, electrolytes) performed in clinical routine in all ELBW infants.

8.5.4 Laboratory Tests

Blood counts and complete blood chemistry is routinely performed according to the local standard of care at the unit at least every 10 +/-4 days until discharge from hospital. No additional blood sampling or analyses will be performed in study subjects in comparison to standard of care of ELBW infants.

All laboratory parameters of interest for the study routinely performed are:

denomination	Variable	time of measurement
Conjugated bilirubin	mg/dL	every 7-14d until discharge
ALAT	U/L	every 7-14d until discharge
ASAT	U/L	every 7-14d until discharge
γ-glutamyltransferase	U/L	every 7-14d until discharge
Alkaline phosphatase	U/L	every 7-14d until discharge
Triglycerides	mg/dL	every 7-14d until discharge

Additional parameters used for the study

All additional parameters of interest are documented or produced routinely during the patient's admission to the unit or follow-up according to the local standard of care. No additional interventions will need to be performed.

denomination	Variable	time of measurement
Basic demographic data		
Sex	m/f	at birth
Gestational age	days	at birth
Twin	yes/no	at birth
Mode of delivery	caesarean/spontaneous	at birth

Prenatal steroids for lung maturation	yes/no	at birth
Birth weight	gram, Z Score	at birth
Birth crown heel length	cm, Z Score	at birth
Birth head circumference	cm, Z Score	at birth
Small for gestational age	yes/no	at birth
Apgar scores at 1, 5 and 10 minutes	0-10	at birth
Umbilical artery pH at birth	range 6.7 – 7.6	at birth

Growth and nutrition parameters

Time on parenteral nutrition	days	at discharge
Total amount of parenteral lipids	gram	at discharge
Enteral nutrition in 1 st first week of life	ml/day	day 0-6
Weight at discharge	gram, Z Score	at discharge from hospital
Crown heel length at discharge	gram, Z Score	at discharge from hospital
Head circumference at discharge	gram, Z Score	at discharge from hospital
Death > 28 days	yes/no	day of life 28 - discharge
(Death before 28 days = drop out)		
If death	day of life	day of life 28 - discharge

Neonatal (preterm) morbidities

Intraventricular hemorrhage Grad 3/4	yes/no	at discharge
Cystic periventricular leucomalacia	yes/no	at discharge
Chronic lung disease	yes/no	at discharge
Received steroids for chronic lung disease	yes/no	at discharge
Treatment for pulmonary hypertension (Sildenafil, iNO)	yes/no	at discharge
Culture proven sepsis	yes/no	at discharge
Necrotizing enterocolitis Bell's Stage ≥ IIa	yes/no	at discharge
Focal intestinal perforation	yes/no	at discharge
Abdominal surgery	yes/no	at discharge
Ibuprofen for PDA	yes/no	at discharge
Surgical ligation of PDA	yes/no	at discharge
Highest ROP Grade	0-5	at discharge
ROP treated with laser	yes/no	at discharge

ROP treated with anti VEGF yes/no at discharge

Other parameters

Length of hospital stay days at discharge

Age at discharge days at discharge

Other investigations

Cerebral function monitoring % continuous pattern weekly

Visual evoked potentials N2 latency in ms at 34-37 wks gestational age

Assessment of neurodevelopmental outcome

Bailey Scales of Infant Development III metric (points) at 12 and 24 months of

Gross motor development 0-5 points corrected gestational age.

Ophthalmologic exams at follow up

Visual fixation yes/no at 12 and 24 months of

Tracking movements yes/no corrected gestational age.

Strabism yes/no

Refraction measured by skiascopy metric (dioptries)

Binocular visualization (Lang Stereo test) pos/neg at 24 months of
corrected gestational age

9. SAFETY DEFINITIONS AND REPORTING REQUIREMENTS

9.1 Adverse events (AEs)

9.1.1 Summary of known and potential risks of the study drug

Undesirable effects observed during the administration of fat emulsions:

	Common (≥1/100 to <1/10)	Uncommon (≥1/1000 to <1/100)	Rare (≥1/10000 to <1/1000)	Very rare (<1/10000)
Respiratory, thoracic and mediastinal disorders			Dyspnoea	
Gastrointestinal		Lack of appetite,		

disorders		nausea, vomiting		
Vascular disorders			Hypotension, hypertension	
General disorders and administration site conditions	Slight increase in body temperature	Chills	Hypersensitivity- reactions (e.g. anaphylactic or anaphylactoid reactions, skin rash, urticaria, flush, headache), heat or cold sensation, paleness, cyanosis, pain in the neck, back, bones, chest and loins	
Reproductive system disorders				Priapism

9.1.2 Definition of adverse events

An AE is any untoward adverse change from the subject's baseline condition, i.e., any unfavorable and unintended sign including an abnormal laboratory finding, symptom or disease which is considered to be clinically relevant by the physician that occurs during the course of the study, whether or not considered related to the study drug.

Adverse events include:

- Exacerbation of a pre-existing disease.
- Increase in frequency or intensity of a pre-existing episodic disease or medical condition.
- Disease or medical condition detected or diagnosed after study drug administration even though it may have been present prior to the start of the study.
- Continuous persistent disease or symptoms present at baseline that worsen following the start of the study.
- Lack of efficacy in the acute treatment of a life-threatening disease.
- Events considered by the investigator to be related to study-mandated procedures.
- Abnormal assessments, e.g., ECG and physical examination findings, must be reported as AEs if they represent a clinically significant finding that was not present at baseline or worsened during the course of the study.
- Laboratory test abnormalities must be reported as AEs if they represent a clinically significant finding, symptomatic or not, which was not present at baseline or worsened during the course of the study or led to dose reduction, interruption or permanent discontinuation of study drug.

Adverse events do not include:

- Pre-planned interventions or occurrence of endpoints specified in the study protocol are not considered AE's, if not defined otherwise (eg.as a result of overdose)

- Medical or surgical procedure, e.g., surgery, endoscopy, tooth extraction, transfusion. However, the event leading to the procedure is an AE. If this event is serious, the procedure must be described in the SAE narrative.
- Pre-existing disease or medical condition that does not worsen.
- Situations in which an adverse change did not occur, e.g., hospitalizations for cosmetic elective surgery or for social and/or convenience reasons.
- Overdose of either study drug or concomitant medication without any signs or symptoms. However, overdose must be mentioned in the Study Drug Log.

9.2 Serious Adverse Events (SAEs)

A Serious Adverse Event (SAE) is defined by the International Conference on Harmonization (ICH) guidelines and WHO GCP guidelines as any AE fulfilling at least one of the following criteria:

- Results in deaths.
- Life-threatening – defined as an event in which the subject was, in the judgment of the investigator, at risk of death at the time of the event; it does not refer to an event that hypothetically might have caused death had it been more severe.
- Requiring subject's hospitalization or prolongation of existing hospitalization – inpatient hospitalization refers to any inpatient admission, regardless of length of stay.
- Resulting in persistent or significant disability or incapacity (i.e., a substantial disruption of a person's ability to conduct normal life functions).
- Congenital anomaly or birth defect.
- Is medically significant or requires intervention to prevent at least one of the outcomes listed above.

Life-threatening refers to an event in which the subject was at risk of death at the time of the event. It does not refer to an event that hypothetically might have caused death if it were more severe. Important medical events that may not immediately result in death, be life-threatening, or require hospitalization may be considered as SAEs when, based upon appropriate medical judgment, they may jeopardize the subject and may require medical or surgical intervention to prevent one of the outcomes listed in the definitions above.

9.2.1 Hospitalization – Prolongation of existing hospitalization

Hospitalization is defined as an overnight stay in a hospital unit and/or emergency room.

An additional overnight stay defines a prolongation of existing hospitalization.

Hospitalization as criterium for SAE classification severely limited in this study. In this study, patients are hospitalized from study start until end of treatment. Hospitalization – prolongation of existing hospitalization should be applied as criterium for SAE classification only in case of AEs directly leading to a prolongation of hospitalization.

The criterium should not be applied to AEs occurring during the routine hospitalization.

The following is not considered an SAE and should be reported as an AE only:

- Treatment on an emergency or outsubject basis for an event not fulfilling the definition of seriousness given above and not resulting in hospitalization.

The following reasons for hospitalizations are not considered AEs, and therefore not SAEs:

- Hospitalizations for cosmetic elective surgery, social and/or convenience reasons.
- Standard monitoring of a pre-existing disease or medical condition that did not worsen, e.g., hospitalization for coronary angiography in a subject with stable angina pectoris.
- Elective treatment of a pre-existing disease or medical condition that did not worsen, e.g., hospitalization for chemotherapy for cancer, elective hip replacement for arthritis.

9.2.2 SAEs related to study-mandated procedures

Such SAEs are defined as SAEs that appear to have a reasonable possibility of causal relationship (i.e., a relationship cannot be ruled out) to study-mandated procedures (excluding administration of study drug) such as discontinuation of subject's previous treatment during a washout period, or complication of a mandated invasive procedure (e.g., blood sampling, heart catheterization), or car accident on the way to the hospital for a study visit, etc.

9.2.3 Suspected unexpected serious adverse reactions (SUSARs)

SUSARs are all serious adverse reactions with suspect causal relationship to the study drug that is unexpected (not previously described in the SmPC - Summary of Product Characteristics or Investigator's brochure) and serious.

9.3 Severity of adverse events

The severity of clinical AEs is graded on a three-point scale: mild, moderate, severe, and reported on specific AE pages of the CRF.

If the severity of an AE worsens during study drug administration, only the worst intensity should be reported on the AE page. If the AE lessens in intensity, no change in the severity is required.

If an AE occurs during a washout or placebo run-in phase and afterwards worsens during the treatment phase, a new AE page must be filled in with the intensity observed during study drug administration.

Mild

Event may be noticeable to subject; does not influence daily activities; the AE resolves spontaneously or may require minimal therapeutic intervention;

Moderate

Event may make subject uncomfortable; performance of daily activities may be influenced; intervention may be needed; the AE produces no sequelae.

Severe

Event may cause noticeable discomfort; usually interferes with daily activities; subject may not be able to continue in the study; the AE produces sequelae, which require prolonged therapeutic intervention.

A mild, moderate or severe AE may or may not be serious. These terms are used to describe the intensity of a specific event (as in mild, moderate, or severe myocardial infarction). However, a severe event may be of relatively minor medical significance (such as severe headache) and is not necessarily serious. For example, nausea lasting several hours may be rated as severe, but may not be clinically serious. Fever of 39°C that is not considered severe may become serious if it prolongs hospital discharge by a day. Seriousness rather than severity serves as a guide for defining regulatory reporting obligations.

9.4 Relationship to study drug

For all AEs, the investigator will assess the causal relationship between the study drug and the AE using his/her clinical expertise and judgment according to the following algorithm that best fits the circumstances of the AE:

Unrelated

- May or may not follow a reasonable temporal sequence from administration of the study product
- Is biologically implausible and does not follow known response pattern to the suspect study drug (if response pattern is previously known).
- Can be explained by the known characteristics of the subject's clinical state or other modes of therapy administered to the subject.
- Unlikely
- May or may not follow a reasonable temporal sequence from administration of the study product
- Is biologically not very plausible
- May be explained by the known characteristics of the subject's clinical state or other modes of therapy administered to the subject.

Possible related

- Follows a reasonable temporal sequence form administration of the study drug.
- May follow a known response pattern to the study drug (if response pattern is previously known).
- Could not be reasonably explained by the known characteristics of the subject's clinical state or other modes of therapy administered to the subject, if applicable.
- Probable
- Follows a reasonable temporal sequence form administration of the study drug.
- Follows a known response pattern to the study drug (if response pattern is previously known).
- other causes for the event are unlikely

Definitely related

- Follows a reasonable temporal sequence form administration of the study drug.
- Follows a known response pattern to the study drug (if response pattern is previously known).
- No other reasonable cause is present.

9.5 Reporting procedures

A special section is designated to adverse events in the case report form. The following details must thereby be entered:

- Type of adverse event
- Start (date and time)
- End (date and time)
- Severity (mild, moderate, severe)
- Serious (no / yes)
- Unexpected (no / yes)
- Outcome (resolved, ongoing, ongoing – improved, ongoing – worsening)
- Relation to study drug (unrelated, possibly related, definitely related)

Adverse events are to be documented in the case report form in accordance with the above mentioned criteria.

9.5.1 Reporting procedures for SAEs

In the event of serious, the investigator has to use all supportive measures for best patient treatment. A written report is also to be prepared and made available to the clinical investigator immediately. The following details should at least be available:

- Patient initials and number
- Patient: date of birth, sex, ethical origin
- The suspected investigational medical product (IMP)
- The adverse event assessed as serious
- Short description of the event and outcome

If applicable, the initial report should be followed by the Follow up report, indicating the outcome of the SAE.

9.5.2 Reporting procedures for SUSARs

It must be remembered that the regulatory authorities, and in case of SUSARs which could possibly concern the safety of the study participants, also the Institutional Review Board / Independent Ethics Committee (IRB / IEC) are to be informed. Such reports shall be made by the study management and the following details should be at least available:

- Patient initials and number
- Patient: date of birth, sex, ethical origin
- Name of investigator and investigating site
- Period of administration
- The suspected investigational medical product (IMP)
- The adverse event assessed as serious and unexpected, and for which there is a reasonable suspected causal relationship to the IMP

- Concomitant disease and medication
- Short description of the event:
 - Description
 - Onset and if applicable, end
 - Therapeutic intervention
 - Causal relationship
 - Hospitalization or prolongation of hospitalization
 - Death, life-threatening, persistent or significant disability or incapacity

Electronic reporting should be the expected method for reporting of SUSARs to the competent authority. In that case, the format and content as defined by Guidance (28) should be adhered to. The latest version of MedDRA should be applied. Lower level terms (LLT) should be used.

9.5.3 Annual Safety Report

The Annual Safety Report will be provided by the principal investigator at least once a year. This report will also be presented annually to the Independent Ethics (IEC) and to the competent authorities by the sponsor.

10.FOLLOW-UP

10.1 Follow-up of study participants including follow-up of adverse events

All study participants will be followed up to 24 months of corrected gestational age to assess neurodevelopment, growth parameters and ophthalmologic exams (visual development (according to the standards of our follow – up outpatient clinic for extremely premature infants. SAEs including death will be monitored. Adverse events will be followed until they have been completely resolved or stabilized according to the investigators discretion.

10.2 Treatment after end of study

There is no treatment after the end of the study

11.STATISTICAL METHODOLOGY AND ANALYSIS

11.1 Analysis sets

Two different analysis sets are defined:

(Modified) Intention to treat set

This analysis set includes all subjects where the outcome can be calculated (more than two blood samples taken), even though the subject was not observed the full 18 weeks.

Per-protocol set

This analysis set comprises all subjects who were observed the full 18 weeks, received the study drug as planned and did not violate the protocol in a way that might affect the evaluation of the effect of the study drug on the primary objective, i.e., without major protocol violations.

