STUDY PERIODS	
 Operational Phase: The operational phase of the study will last for three years (months 1-39) and start with the inclusion of the first patient to the trial and will end with the last patient's discharge from hospital. Follow Up: The follow up phase will last start with the first included patient reaching the age of 12 months corrected age and will end at 24 months of corrected gestational age of the last included patient (months 15-62) 					
INVESTIGATIONAL DRUG	SMOFLIPID®:					

	initial dose: 1g/kg/day target dose: 3g/kg/day
COMPARATIVE DRUG /CONTROL CONDITION	INTRALIPID® initial dose: 1g/kg/day target dose: 3g/kg/day
CONCOMITANT MEDICATION	In case of of cholestasis (i.e. conjugated bilirubin two times > 1.5 mg/dl), ursodeoxycolic acid at 20-30 mg/kg/day is the treatment of choice. In case of severe cholestasis (i.e. conjugated bilirubin > 6 mg/dL) and elevation of liver enzymes (3 times over normal) a rescue therapy using pure fish oil (Omegaven®) at 0.5-1 g/kg/day will be allowed.
EFFICACY ENDPOINT	Incidence of parenteral nutrition associated cholestasis (PNAC), defined as conjugated bilirubin > 1.5 mg/dl measured on two consecutive occasions by blood sampling performed at least every 10 +/- 4 days. Based on a present incidence of 25 % using the comparative drug at the study center (unpublished data 2007-9) an absolute difference of 15 % between the groups (25% vs. 10% incidence) was considered clinically significant.
TOLERABILITY / SAFETY ENDPOINTS	-
PHARMACOKINETIC / PHARMACODYNAMIC ENDPOINTS	-
QUALITY OF LIFE / PHARMACOECONOMIC ENDPOINTS	-

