7.1.4 Study duration

The interventional phase starts with randomization on the study drug in the first 5 days of life and ends with discontinuation of PN, typically after 6 weeks (mean 44 days +/- SD 34 days, personal data).

The follow up phase ends at 24 months (2 years) of corrected gestational age.

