11.5 Missing, unused and spurious data

If less than two blood samples of a patient were taken, the outcome cannot be calculated and therefore, this patient will be excluded from the analysis. The analysis will be carried out per protocol.

If the outcome of a patient can be calculated (more than two blood samples taken) but the patient was withdrawn from the study before week 18, analysis will be carried out 1) by intention to treat analysis, with the duration of treatment as additional covariable and 2) per protocol.

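### The per-protocol set demands 18 weeks of observation although the endpoint is followed only to discharge, and the sample-count rule for the modified intention-to-treat set contradicts itself

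*Combined protocol and SAP*

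**What the plan says.** **Per-protocol set.** Section 11.1: "This analysis set comprises all subjects who were observed the full 18 weeks, received the study drug as planned", with no major protocol violation. No time margin is attached to the 18 weeks.

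**Observation and completion.** Section 8.5.3: "At discharge of the patient from hospital, patients undergo the end-of-study examination". Section 8.5.4 likewise schedules bilirubin only up to discharge. Section 7.1.5 treats an infant as prematurely discontinued when the EOS examination or pivotal assessments are missed. Treatment, under 7.1.4, "ends with discontinuation of PN, typically after 6 weeks (mean 44 days +/- SD 34 days, personal data". Table 1, by contrast, puts the End of Study visit at week 18.

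**mITT set.** Section 11.1: "This analysis set includes all subjects where the outcome can be calculated (more than two blood samples taken". It explicitly keeps infants not observed for 18 weeks. Section 7.1.5 repeats the more-than-two condition. Section 11.5 uses a different threshold for exclusion: "If less than two blood samples of a patient were taken, the outcome cannot be calculated". The synopsis endpoint is PNAC, "defined as conjugated bilirubin > 1.5 mg/dl measured on two consecutive occasions by blood sampling performed at least every 10 +/- 4 days".

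**Which set leads.** For an infant with a calculable outcome, 11.5 continues: "but the patient was withdrawn from the study before week 18, analysis will be carried out 1) by intention to treat analysis", and then lists a per-protocol analysis as the second step. The synopsis has an entry for the main analysis set but names none, and neither does 11.6.1.

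**The concern.** A per-protocol set is meant to hold infants who were treated and assessed as planned. Going home early after full treatment and a completed EOS examination is not a deviation, yet the 18-week condition treats it as disqualifying. Length of stay is determined after randomisation, is plausibly related to cholestasis, and may be affected by treatment. Conditioning on it can bias the comparison as well as shrink it.

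The sample-count rule raises a smaller issue. Two consecutive raised values settle the outcome, but three samples are needed to enter the mITT set. An infant with exactly two samples is neither admitted by 11.1 nor excluded by 11.5.

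Because no set is named as primary, these ambiguities could be settled after the data have been seen.

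**Working it through.** **1. The plan's own figure.** Inputs from the synopsis and 11.2: 25% versus 10%, two-sided 0.05, 80% power, 1:1. The mean rate is 0.175.

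n per group = [1.960·√(2·0.175·0.825) + 0.842·√(0.25·0.75 + 0.10·0.90)]² / 0.15² = (1.053 + 0.443)² / 0.0225 ≈ 99.5, so 100. The stated 100 per group is reproduced. Power at 100 is Φ[(0.15·√100 − 1.053)/0.527] = 80.2%.

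**2. Who fails the 18-week condition.** Take an infant whose PN has stopped and who is discharged at week 12 with the EOS examination done.

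- 7.1.5 with 8.5.3: completed.
- 8.5.4: sampled for the whole planned window.
- 11.1, per-protocol: not observed for 18 weeks, so out.
- 11.1, mITT: in.

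An infant withdrawn before week 18 is sent by 11.5 to a per-protocol analysis, although 11.1 bars that infant from the set.

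**3. Does treatment or stay decide membership?** 18 weeks = 126 days, and (126 − 44)/34 = 2.4 SD above mean PN duration. With that mean and SD, the share still on PN at day 126 is about 1% under a normal distribution and about 3% under a lognormal or gamma. Almost every infant will have finished study drug by then, so passing the condition depends on still being in hospital.

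**4. The planning timeline.** The synopsis puts the last infant's first visit at month 36. It also says "The operational phase of the study will last for three years (months 1-39" and ends that phase with the last discharge. 39 − 36 = 3 months, about 13 weeks, against 18. These are round planning months for one infant. They show that the plan expects discharge before week 18 to be possible, but they give no distribution of stay.

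**5. Effect on numbers.** The share leaving before week 18 is an assumption. Event rates are held at 25% and 10%, although selection on stay could change them.

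| Leaving before week 18 | Per-protocol n per group | Power |
|---|---|---|
| 0% | 100 | 80.2% |
| 10% | 90 | 75.9% |
| 20% | 80 | 70.8% |
| 30% | 70 | 64.9% |
| 50% | 50 | 50.6% |

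**6. Exactly two samples.** Baseline bilirubin above 1.5 mg/dl is an exclusion (7.1.3), so a baseline value can never be one of the two raised values.

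- *Baseline counted:* more than two means baseline plus two later samples, the minimum for observing PNAC. No confirmed case is lost.
- *Baseline not counted:* an infant with two raised post-randomisation values is a confirmed case but outside the mITT set. With the first such sample one interval after day 0, the exactly-two window runs from day 12 to 18 (6-day interval), 20 to 30 (10-day) or 28 to 42 (14-day). The infant must leave the study within that window.

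If 1% to 5% of infants had exactly two samples, mITT power from 100 per group would be 79.8% to 78.1%. The documents do not say which counting applies. The mismatch between 11.1 and 11.5 exists under both.

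**The case against.** The best defence is that 18 weeks is shorthand for EOS. Table 1 labels the week 18 visit End of Study, apparently with a margin of one month (the row is broken in the text), and 7.1.5 defines completion by EOS. This may be what was intended, but 11.1 does not say it: it requires the full 18 weeks and uses the same fixed period when describing the mITT set. A one-month margin gives 126 − 30 = 96 days, or 13.7 weeks, so an infant discharged at week 12 still fails. If EOS is meant, the remedy is to write EOS.

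A second defence is that 11.4 leaves major and minor deviations, and their link to the analysis sets, to a SAP. That does not help, because early discharge is not a deviation and the 18-week condition is already fixed in 11.1.

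Other objections stand and limit the point. The mITT set keeps infants discharged early, and 11.5 lists intention to treat first, so the 18-week condition harms only the per-protocol result. PN duration is not length of stay.

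A reader might go further in three ways that the documents do not support:

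- **That most of the per-protocol set is lost, or that mainly the sickest infants remain.** Without age at discharge, neither can be shown.
- **That the mITT set plainly drops infants with a known outcome.** An infant sampled only on days 0 and 14 cannot be a case, because a raised baseline is an exclusion. The loss arises only if baseline is not counted.
- **That the sample rule is what removes early deaths.** Deaths before day 28 are withdrawn under a separate rule in 7.1.5, and 8.5.4 also records them as drop-outs.

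**Conclusion.** The point holds in a limited form. As written, the per-protocol set removes infants who completed treatment and EOS before week 18 and so selects on a post-randomisation variable. Table 1 and 8.5.3 disagree on when EOS occurs, and 11.5 contradicts 11.1 on infants withdrawn before week 18. The size of the loss is unknown, and the power figures above illustrate assumed shares only.

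The sample-count conflict is real but narrower. It costs a confirmed case only if baseline is not counted and the infant leaves between the second and third post-randomisation samples, which should be uncommon. With no primary set named, both matters should be settled before unblinding. This is a change that should be made; it does not invalidate the main comparison.

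**What to change.** - **11.1:** define per-protocol observation as lasting until discharge (EOS examination) and drop the fixed 18 weeks.
- **11.5:** replace the week 18 cut-off with EOS, and state that withdrawn infants enter the per-protocol analysis only if they meet its definition.
- **Table 1 and 8.5.3:** reconcile the timing of EOS.
- **7.1.5, 11.1 and 11.5:** use one sample rule, namely at least two post-randomisation conjugated bilirubin samples, or PNAC already met. The words post-randomisation are essential. A bare two-or-more rule would admit infants with baseline plus one later value, who cannot be cases and would be scored as non-events. Reconcile the rule with the day-28 withdrawal and replacement text in 7.1.5.
- **11.1 and 11.6.1:** name the mITT set as primary and the per-protocol set as a sensitivity analysis.

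The cost is wording in a few sections and one table. No new data, visits or blood samples are needed. Tabulating age at discharge by group, from data already collected, would show how many infants the 18-week condition would have removed.
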